3 STUDY OBJECTIVES AND DESIGN

3.1 Primary objective and hypothesis

Quantification of physical activity (daily steps) during the first two weeks after hospital discharge as a predictor for MACE at one year.

Hypothesis I: Daily steps measured during the first two weeks after hospital discharge from PCI is a significant independent predictor additional to traditional risk factors for MACE at one year after PCI.

Secondary objectives and hypothesis

1. Comparison between daily steps and objectively measured activity counts (divided in time spent in moderate-to-vigorous activity, light activity and sedentary activity), as well as patient reported activity:

Hypothesis I: Objectively monitored activity counts two weeks after hospital discharge is significantly associated with daily step counts and self-reported activity level

Hypothesis II: Predictive value of daily step count during the first two weeks after hospital discharge is significantly better than the predictive value by patient reported physical activity for MACE at 12 months.

2. Association of daily steps after one year with reaching targets for systolic blood pressure, low-density lipoprotein cholesterol (LDL-C), body mass index (BMI) and glycated haemoglobin (HbA1c):

Hypothesis I: Patients with higher daily step counts during the first two weeks after hospital discharge have higher achievement rates of target levels at 12 months for blood pressure, body weight, blood lipids, and blood sugar.

3. Comparison of daily steps after hospital discharge and MACE between non cardiac rehabilitation (CR), conventional hospital based CR, tele-CR and modular CR participants.

Hypothesis I: Tele-rehabilitation and conventional CR patients achieve higher daily step counts (corrected for age, risk factors and comorbidities) at two weeks after PCI than patients who decline any form of CR.

Hypothesis II: Tele-rehabilitation and conventional CR patients a lower risk of MACE within one year than patients who decline any form of CR

4. Comparison of daily steps at one year after hospital discharge in different CR groups.

Hypothesis I: Tele-rehabilitation is not inferior to conventional ambulatory cardiac rehabilitation (CR) in increasing daily steps from two weeks after PCI to 12 months after PCI

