5 STATISTICS AND METHODOLOGY

5.1. Statistical analysis plan and sample size calculation

Predictive value of daily steps during the first two weeks after hospital discharge is quantified by net reclassification improvement (NRI) and by increase of area under the curve (AUC) of the receiver operating characteristic curve (ROC) of a model consisting of traditional risk factors (age, sex, cardiovascular risk factors, cardiovascular history, comorbidities).

Descriptive statistics are used to quantify and characterise the populations who choose conventional hospital based CR, tele-rehabilitation, and modular CR in terms of number, age, sex, medical history, cardiovascular risk factors and comorbidities. MACE at one year follow-up and daily steps during the first two weeks after hospital discharge will be compared between the CR and non CR participants using multivariate modelling adjusted for potential confounding factors. Further, for patients who perform their yearly routine follow-up visit at our centre, data on body mass index (BMI), systolic blood pressure (BP), low-density lipoprotein cholesterol (LDL-C) and smoking cessation will be derived from the clinic's patient information system and compared between different forms of CR. Also, daily steps after 12 months from patients who volunteer to monitor steps again will be quantified for the different CR groups and tested between the groups if sufficient data can be gathered. The same will be done for changes in daily steps between the first two weeks after hospital discharge and at 12 months.

Sample Size:

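### Secondary objective 3 compares four CR groups and its hypotheses name tele-CR and conventional CR, but section 5.1 plans only CR versus non-CR for early steps and MACE and does not place modular CR

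*SAP*

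**What the plan says.** Section 3.1 of the SAP, repeated in the synopsis, sets secondary objective 3 as "Comparison of daily steps after hospital discharge and MACE between non cardiac rehabilitation (CR), conventional hospital based CR, tele-CR and modular CR participants". That is four groups and two outcomes.

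Two hypotheses follow, both against patients who decline CR altogether:

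- Hypothesis I, on early steps: "Tele-rehabilitation and conventional CR patients achieve higher daily step counts (corrected for age, risk factors and comorbidities) at two weeks after PCI".
- Hypothesis II, on MACE: "Tele-rehabilitation and conventional CR patients a lower risk of MACE within one year than patients who decline any form of CR".

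Section 5.1 gives the analysis. MACE at one year and steps in the first two weeks "will be compared between the CR and non CR participants using multivariate modelling adjusted for potential confounding factors".

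Section 5.1 separates the forms of CR in three other places:

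- a descriptive account of the "populations who choose conventional hospital based CR, tele-rehabilitation, and modular CR in terms of number, age, sex, medical history" and further baseline features;
- 12-month risk factors, "derived from the clinic's patient information system and compared between different forms of CR";
- 12-month steps, which "will be quantified for the different CR groups and tested between the groups if sufficient data can be gathered", with the same planned for change in steps.

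**The concern.** The objective, its hypotheses and the analysis stand in one document and do not describe the same comparison. The objective has four groups, the hypotheses have two named forms against decliners, and the analysis has CR against non-CR. An analyst who follows section 5.1 to the letter produces an estimate for a group that no hypothesis describes.

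Two things are at stake. If modular CR patients count as CR participants and their outcomes differ from those of the other two forms, the estimate moves away from the forms that Hypotheses I and II name. And if the grouping is settled only at analysis, several defensible groupings are available for the same directional hypotheses, and the choice among them could follow the data.

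**Working it through.** The point rests on comparing text. The arithmetic only illustrates it.

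**Step 1. Groups, place by place**

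| Place in SAP | Outcomes | Groups |
|---|---|---|
| 3.1, objective 3 (and synopsis) | early steps, MACE | none, conventional, tele, modular |
| 3.1, Hypotheses 3.I and 3.II | early steps; MACE | tele and conventional versus decliners |
| 2, last paragraph on risk prediction | steps, MACE | CR versus no CR |
| 2, same paragraph | steps only | between types of CR |
| 5.1 | MACE, early steps | CR versus non-CR |
| 5.1 | baseline features | by form, descriptive |
| 5.1 | 12-month BMI, systolic BP, LDL-C, smoking cessation | between forms of CR |
| 5.1 | 12-month steps, change in steps | between CR groups, tested if data suffice |

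The by-form rows of 5.1 do not cover MACE or early steps. The four-group comparison of objective 3 therefore has no analysis.

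**Step 2. Where modular CR falls**

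Section 5.1 does not define a CR participant. It lists modular CR beside the other two forms, section 8.1 counts three forms of CR, and no section excludes modular patients from the CR side. The natural reading is that they are in it. The hypotheses do not include them.

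**Step 3. The plan's own event count**

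Inputs from 5.1: HR 2.66, significance level 0.05, power 80%. The two-sided Schoenfeld formula with equal groups gives (1.960 + 0.842)² / (0.25 × (ln 2.66)²) = 32.8, so 33 events, as stated. Doubling gives 66, and 66 / 0.08 = 825 patients. These figures concern activity quartiles, not CR groups. They matter here only because about 66 MACE are available for objective 3.

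**Step 4. Illustration of pooling**

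Assumed, not in the document: a true MACE ratio of 0.70 for tele-CR and conventional CR, 1.0 for modular CR, equal baseline risk, and modular share m of CR patients. Pooled ratio = (1 − m) × 0.70 + m × 1.0.

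- m = 0.20: 0.56 + 0.20 = 0.76
- m = 0.33: 0.469 + 0.33 = 0.80
- m = 0.50: 0.35 + 0.50 = 0.85

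**Step 5. What separate contrasts cost for MACE**

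Assumed: half of patients in CR, an equal split over three forms, equal risk. Of 66 events, 33 fall in the non-CR group and 33 / 3 = 11 in each form. The approximate unadjusted standard error of the log ratio is √(1/a + 1/b), for a and b events in the two groups. The 95% limits are the estimate divided and multiplied by exp(1.96 × SE).

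- One form versus none: √(1/11 + 1/33) = 0.348, factor 1.98
- Tele plus conventional versus none: √(1/22 + 1/33) = 0.275, factor 1.72
- All CR versus none: √(1/33 + 1/33) = 0.246, factor 1.62

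Under these assumptions the joint contrast matches the hypothesis and loses little precision against full pooling. Single-form contrasts lose much more.

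**The case against.** The strongest reply has four parts.

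First, section 5.1 never says that the forms are coded as one level or that modular CR is included. This stands: a reader might infer that the plan expressly collapses all forms, but the inclusion of modular CR is an inference, though the natural one. If exclusion was meant, 5.1 has to say so.

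Second, a reader might take the hypotheses as requiring each named form to be tested separately against decliners, and conclude that neither is compared with non-CR at all. The wording equally allows tele-CR and conventional CR taken jointly. On that reading both forms are inside the planned contrast and only the place of modular CR is open. The mismatch shrinks but remains.

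Third, the background states the MACE aim as CR versus non-CR, so 5.1 follows an aim of the document. This also stands. It shows that two versions of the question coexist, and that changing the objective would resolve the conflict as well as changing the analysis.

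Fourth, section 3.3 calls the study exploratory, and with about 66 MACE pooling is defensible. This bears on severity and on the choice of MACE contrast. It does not remove the need for directional hypotheses to have a matching analysis.

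**Conclusion.** The point holds as an inconsistency on a secondary objective. For early steps and MACE, section 5.1 as written neither makes the four-group comparison of objective 3 nor tests the group named in Hypotheses 3.I and 3.II.

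A reader might go further and infer that no planned analysis gives any result for tele-CR or conventional CR. The document does not support that, because by-form comparisons are planned for 12-month risk factors, 12-month steps and change in steps. The gap is limited to early steps and MACE.

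The size is unknown. The document gives no uptake by form and no CR effect, and does not suggest that modular CR acts differently. The ratios of 0.76 to 0.85 rest wholly on assumed inputs. The primary analysis and the sample size are unaffected, so this is a desirable correction rather than an essential one.

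**What to change.** Reconcile sections 3.1 and 5.1 in one of two ways.

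**Option A: change the analysis.**

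- Early steps: fit CR form as a four-level factor with no CR as reference in the adjusted model. Use tele-CR versus none and conventional CR versus none as the contrasts for Hypothesis 3.I.
- MACE: take tele-CR plus conventional CR versus none as the main contrast for Hypothesis 3.II, keep modular CR as a separate level, and report per-form estimates descriptively.
- Both outcomes: report all CR versus none as supportive.

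**Option B: change the objective.** Reword objective 3 and its hypotheses, in section 3.1 and the synopsis, to any CR versus none, in line with the background, and state that modular CR is included.

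Under either option, define the comparator once, since the hypotheses speak of decliners and 5.1 of non-CR participants.

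The cost is wording only, because section 8.2 already provides for data on choice of CR. Option A brings wider intervals than the pooled contrast, most of all for single forms on MACE. Option B gives up any claim about a particular form on these two outcomes.

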3.3 Study design

This is a monocentric open label explorative study (with primary objective to assess the predictive value of daily steps for MACE). Patients will be asked to wear an activity tracker for two weeks following hospital discharge. Patients who participate in any form of CR in our institution and attend the routine check-up 12 month after PCI in our institution will be asked to wear the activity tracker again for two weeks.

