4.4 Withdrawal and discontinuation

Data gathered until withdrawal of consent will be used in coded form. Wearing the activity tracker again after 12 month is voluntary. MACE data derived from CARDIOBASE registry is subject to the CARDIOBASE registry consent, in case of withdrawal of consent for CARDIOBASE MACE and patient related data from this registry will not be used. Health related data from the clinic's patient information system will not be used if patients withdrawal the study IC and the clinic's general informed consent.

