5.2. Handling of missing data and drop-outs

CARDIOBASE has very few missing cases for MACE, therefore, for MACE, a complete case analysis will be done. Activity data will be used when at least 7 days of 12 h/day (during day time) recording are available. Otherwise, these patients will be allocated to a non-compliant group for which patient characteristics will be summarised and compared to the compliant group. Patients of the non-compliant group will not be used for the analysis of the primary endpoint. For secondary outcomes, missing data will be imputed by multiple imputation.

In case of a large number of non-compliant patients (>50), additional patients will be recruited (if necessary recruitment period will be extended).

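### Objective 4 claims non-inferiority of tele-rehabilitation on the increase in daily steps, but SAP section 5.1 plans only an unnamed between-group test, with no margin and no confidence-limit rule

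*SAP*

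**What the plan says.** Hypothesis I of secondary objective 4 (SAP section 3.1) reads: "Tele-rehabilitation is not inferior to conventional ambulatory cardiac rehabilitation (CR) in increasing daily steps from two weeks after PCI to 12 months after PCI".

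Section 5.1 is the only place that describes an analysis of these data. Of 12-month steps from patients who volunteer to be monitored again, it says they "will be quantified for the different CR groups and tested between the groups if sufficient data can be gathered". For the quantity in the hypothesis it adds: "The same will be done for changes in daily steps between the first two weeks after hospital discharge and at 12 months". It does not name the test or single out the tele-versus-conventional contrast among the CR groups.

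The same section states covariate adjustment for a different contrast. One-year MACE and first-two-week steps are to be "compared between the CR and non CR participants using multivariate modelling adjusted for potential confounding factors". Objective 3, Hypothesis I also has an adjusted comparison in mind: CR patients should "achieve higher daily step counts (corrected for age, risk factors and comorbidities) at two weeks after PCI" than patients who decline CR. No adjustment is stated for comparisons between forms of CR.

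Section 2 frames the interest in CR types as a question of whether step counts differ. Section 3.3 calls the study explorative.

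**The concern.** A non-inferiority claim says that any deficit is smaller than a stated amount. It needs that amount, and a rule that sets a confidence limit against it. A test of no difference answers another question, and its failure to reject says little when groups are small or the outcome is variable. Daily steps vary widely between people, and "Wearing the activity tracker again after 12 month is voluntary".

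Followed as written, the plan invites a non-significant between-group test to be reported as evidence that tele-rehabilitation is as good as conventional CR. Patients also choose their form of CR. Unless the comparison is adjusted, a difference, or the lack of one, may reflect who chooses tele-rehabilitation.

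**Working it through.** **1. The plan's own power calculation concerns another question.** Section 5.1 sizes the study on MACE: HR 2.66, significance level 0.05, power 80%. With the Schoenfeld formula, two-sided and with equal groups, events = 4(1.96 + 0.842)² / (ln 2.66)² = 31.4 / 0.957 = 32.8, so 33 as stated. Doubling gives 66, and 66 / 0.08 = 825 patients. These figures reproduce, but none bears on daily steps or on tele-rehabilitation versus conventional CR.

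**2. What each possible result would allow.** Let D be the tele-minus-conventional difference in change in daily steps, and M > 0 a margin that the document does not give.

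| Result for D | Can it be judged against the hypothesis without M? |
|---|---|
| CI wholly above 0 | Yes. The lower limit exceeds any −M, so non-inferiority follows. |
| CI includes 0 | No. It depends on whether the lower limit is above −M. |
| CI wholly below 0, deficit small | No. Tele-rehabilitation is worse, but perhaps by less than M. |

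The gap covers the second and third rows. The second is what one would expect if the two forms perform alike, which is the situation a non-inferiority hypothesis is written for.

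**3. How often a real deficit would go undetected.** The document gives no SD, margin or group size for this comparison, so the rest is illustration. Probability of a non-significant two-sided 5% test = 1 − Φ(d·√(n/2) − 1.96), with d the true deficit in SD units of the change and n assumed per equal group. For example, d = 0.3 and n = 50 gives 1 − Φ(1.50 − 1.96) = 0.677.

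| n per group (assumed) | d = 0.3 | d = 0.5 |
|---|---|---|
| 20 | 84% | 65% |
| 30 | 79% | 51% |
| 50 | 68% | 30% |
| 100 | 44% | 6% |

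**4. Precision in steps per day.** Half-width of the 95% CI = 1.96·SD·√(2/n), with the SD of change assumed at 2500 to 4000 steps/day.

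| n per group (assumed) | SD 2500 | SD 4000 |
|---|---|---|
| 25 | 1386 | 2217 |
| 50 | 980 | 1568 |
| 100 | 693 | 1109 |

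**5. What a formal claim would need.** With true difference 0, one-sided 2.5%, 80% power and equal groups, n per group = 2(1.96 + 0.842)² / m², with m the margin in SD units. For m = 0.3 this is 15.7 / 0.09, so 175. For m = 0.2 it is 393, and for m = 0.5 it is 63.

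**The case against.** The best case for leaving the text alone is that non-inferiority appears in one sentence, under the last secondary objective of an explorative study. The heading of that objective, the synopsis and section 2 all describe a plain comparison. Section 5.1 makes the test conditional on enough data and already promises to quantify steps by CR group, which is close to estimation. All of this is correct. It bears on priority and shows that the non-inferiority wording is the outlier. It does not supply the missing margin.

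It can also be said that the adjustment point rests on silence, since section 5.1 does not exclude adjustment between CR forms. That is fair. Adjustment is therefore offered as part of the remedy for a self-chosen comparison, not as a separate error.

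A reader might infer more than the document supports:

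- **That no result could bear on the hypothesis.** The first row of the table in step 2 shows otherwise.
- **That 12-month steps come only from CR participants.** Section 3.3 limits repeat tracking to "Patients who participate in any form of CR in our institution and attend the routine check-up 12 month after PCI in our institution". The synopsis and sections 3.4 and 4.3 put it to patients attending the 12-month check-up without that condition. Both groups in this comparison are in CR anyway.
- **That the analysis set is contradictory.** Section 5.2 says "For secondary outcomes, missing data will be imputed by multiple imputation", but that is a general sentence. Section 5.1 speaks specifically of volunteers, and the natural reading is that the specific sentence governs.
- **That the comparison is shown to be underpowered.** The SDs, group sizes and margins above are assumptions, and the document projects none of them.

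**Conclusion.** The point holds in a limited form. Section 3.1 states a non-inferiority hypothesis, section 5.1 answers it with an unnamed, conditional between-group test, and the document gives neither a margin nor a confidence-limit rule. Both parts stand in the same document, so this is a mismatch rather than a detail left to a protocol. A significantly larger increase with tele-rehabilitation would support the hypothesis. A non-significant difference could not be read as non-inferiority, and a small significant deficit could not be classified.

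The practical size depends on assumed inputs. With 50 per group, a true deficit of 0.3 SD would be missed about two times in three, and the CI would extend roughly 980 to 1570 steps/day either side of the estimate. The conclusion does not depend on these figures, because the margin is absent at any group size. The primary MACE analysis and the sample size are untouched, so this is a low-priority correction.

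**What to change.** In section 3.1, reword Hypothesis I of objective 4 as an estimation aim: *to estimate the difference between tele-rehabilitation and conventional CR in the change in daily steps from the first two weeks to 12 months*. In section 5.1, replace the unspecified test for this contrast with that difference and its 95% CI. Apply to it the adjustment for potential confounders that 5.1 already states for CR versus non-CR, because CR form is self-chosen.

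Keep the non-inferiority wording only if a margin is justified and fixed before the 12-month data are seen, with the conclusion resting on whether the lower 95% limit lies above minus that margin.

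The cost is a few lines of text and one adjusted estimate on data already planned. The downside is that a claim becomes an estimate.

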3.2 Primary and secondary endpoints

Primary endpoint: Occurrence of MACE within 12 months after PCI

Secondary endpoints: BMI, systolic BP, LDL-C, HbA1c and daily steps two weeks and 12 months after PCI; proportion and patient characteristics of CR participants and non-participants

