3.4. Study intervention

Patients will be informed about the study by the prevention team (advanced nurse practitioners) usually on the day of discharge from PCI during the routine visit by this team to inform patients about the different options of CR. Patients will be provided with an activity tracker in the form of a wrist band, the patient information sheet including informed consent (IC), the IPAQ-SF and an addressed and prepaid envelope. They are asked to read the patient information when arrived at home, sign the IC when willing to participate and wear the wrist band continuously for two weeks after hospital discharge. After that, they should send the wrist band, the filled in IPAQ-SF and signed IC in the provided envelope to our institute. If they are unwilling to participate, they can send the activity tracker back straight away. Patients attending the clinical routine check-up after 12 months in our institution will be asked to wear the activity tracker again for two weeks.

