Based on a study on nearly 9000 PCI patients, physical activity level assessed by the Duke Activity Status Index (DASI) questionnaire found a 4.8-fold increase in future risk of incident major adverse cardiac events at 3 years in the quartile with lowest DASI compared to the highest quartile.(6) The DASI score reclassified 15% of patients ($P<0.001$) beyond traditional risk factors in predicting future MACE.(6) In the approximately 6500 patients with obstructive CAD, the adjusted HR (adjusted for traditional risk factors and history of heart failure and peripheral arterial disease) for MACE in the lowest DASI quartile compared to the highest quartile was 2.66 (95% CI 2.16 to 3.27). According to this relative hazard, 33 events would be needed to reach a significance level of 0.05 and a power of 80% in these two quartiles. For the whole sample this would be 66 events. According to data from CARDIOBASE, in the 10 years from 2009-2018 1083 (8%) of patients younger than 80 years had a MACE between 7 and 365 days after PCI, which corresponds to approximately 100 MACE per year. During the last 3 years (Oct 2015 to Oct 2018), 3683 patients younger than 80 years were recruited for CARDIOBASE, which equates to approximately 1200 potential study patients per year. If we assume that 50% of these patients are willing to participate in our study (wear an accelerometer for 2 weeks after discharge), we could recruit about 600 patients per year, of whom approximately 48 (8%) will have a MACE within 12 months following PCI. To reach 66 MACE we will need to recruit 825 patients which will require

a recruitment period of approximately 16 months.

Statistical analyses will be performed by [name] (CAS in statistics of the University of Bern) using the software R.

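### No start of event counting is set for the primary prediction analysis: MACE counts from PCI, but the step record is complete only 14 days after discharge

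*SAP*

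**What the plan says.** Three parts of the SAP bear on the timing.

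- **Outcome.** Section 3.2: "Primary endpoint: Occurrence of MACE within 12 months after PCI". The synopsis also runs the endpoint from PCI.
- **Predictor.** The primary hypothesis in section 3.1 is that "Daily steps measured during the first two weeks after hospital discharge from PCI is a significant independent predictor" of MACE beyond traditional risk factors. Section 5.1 measures this by NRI and by the increase in AUC over a traditional risk-factor model.
- **Analysis set.** Section 5.2: "Activity data will be used when at least 7 days of 12 h/day (during day time) recording are available". Otherwise the patient is classed as non-compliant, and "Patients of the non-compliant group will not be used for the analysis of the primary endpoint". The reason for short wear plays no part in this rule.

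On the return of devices, section 3.4 says of the two weeks of wear: "After that, they should send the wrist band, the filled in IPAQ-SF and signed IC in the provided envelope to our institute".

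The sample-size text in section 5.1 takes its 8% from patients who "had a MACE between 7 and 365 days after PCI" and applies it to 600 recruits a year, "of whom approximately 48 (8%) will have a MACE within 12 months following PCI".

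The eligibility criteria (4.1), the analysis text (5.1) and the missing-data rules (5.2) contain no landmark, no requirement to be event-free when the step record closes, and no rule for a MACE between PCI and the end of wear.

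**The concern.** The study asks whether early steps identify patients who will later have a MACE, so that they can be followed more closely. That use begins once the steps are known. An event that comes before or during the step record is not predicted by it, and it may itself lower the count.

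The wear rule treats early events unevenly:

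- **Event on wear days 1-7.** Seven full days cannot yet exist. If wear stops or is interrupted for long, the patient leaves the primary analysis because of the outcome. If wear resumes soon enough, the patient stays in with a record made mostly after the event.
- **Event on wear days 8-14.** Seven valid days may already exist. The patient stays in, with a record that may run past the event.
- **Event before discharge.** On the wording of section 3.2 it counts, if CARDIOBASE records it as MACE. All the steps then follow the event.

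Adjusting for baseline risk factors removes none of this. At stake is whether the AUC increase and NRI can be read as prediction. Without a rule, the sponsor could not show afterwards that the effect was small.

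**Working it through.** **1. The plan's own figures.** Section 5.1 gives HR 2.66, significance level 0.05 and power 80%. With Schoenfeld's formula, two-sided, equal groups:

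events = 4 × (1.960 + 0.842)² / (ln 2.66)² = 32.8, so 33.

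Twice 33 is 66 events; 66 / 0.08 = 825 patients; 825 / 600 × 12 = 16.5 months. All agree with the SAP.

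**2. Events in the wear window.** The SAP gives no event timing. Assume a constant hazard, and apply the rate for days 7-365 (359 days) to every wear day:

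- 66 / 359 = 0.184 events per day
- 14 wear days: 14 × 0.184 = 2.6 events
- days 1-7: 7 × 0.184 = 1.3 events (exclusion possible)
- days 8-14: 1.3 events (patient can stay in)

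**3. Effect on the analysis if window events are retained.** Simulation with no true effect of steps: N = 825, 66 events, base risk score with AUC 0.70 (assumption), steps standard normal, and *k* events with steps lowered by *s* SD (assumption). There were 8,000 runs per setting, so the Monte Carlo standard error near 5% is √(0.05 × 0.95 / 8000), about 0.24 percentage points.

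| Retained events *k* | Type I error at *s* = 0.4 / 1 / 2 |
|---|---|
| 0 | 5.1% |
| 1 | 5.1 / 5.9 / 5.3% |
| 2 | 5.2 / 5.9 / 7.3% |
| 3 | 4.8 / 6.3 / 10.2% |

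The test is the likelihood-ratio test for steps added to the base score. The mean AUC increase is 0.0028-0.0039 for *k* = 1-3, against 0.0029 with none. Continuous NRI is 0.084-0.088, against 0.085.

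A hand check gives the same picture. The test statistic shifts by (*k* × *s* / 66) / √(1/66 + 1/759). For *k* = 2, *s* = 1 this is 0.24, giving a two-sided error of 5.6%. For *k* = 3, *s* = 2 it is 0.71, giving 10.9%.

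**4. Cost of a landmark.** Let discharge fall *d* days after PCI (not given; assume 0-7). The landmark is day *d* + 14. Of the 66 planned events, counted from day 7, it removes 0.184 × (*d* + 7):

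- *d* = 0: 1.3 lost, 64.7 left
- *d* = 7: 2.6 lost, 63.4 left

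Half the events are taken to lie in the two outer quartiles, as the SAP does. Power = Φ(√(events / 8) × ln 2.66 − 1.96): 80.2% at 66 events, 79.6% at 65, 78.4% at 63.

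If 5-20% of events came before the landmark (assumption), 62.7 to 52.8 would remain, with power 78% to 71%.

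**The case against.** The strongest reply is that the harm is slight and partly contained already. The measures named in section 5.1 hardly change. The band and consent come back only after the wear period, so most patients who die during wear would not enter. Section 5.2 compares non-compliant with compliant patients. The study calls itself explorative. Much of this stands, and it limits the size of the point. But neither the mail-back nor the comparison decides which early events count.

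Four stronger readings are tempting, and the documents do not support them.

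- **Type I error doubles to 10%.** This needs three retained events, each with steps 2 SD lower. Only about 1.3 events are expected on days 8-14. With continuous wear, at least 7 of those patients' 14 days precede the event, so a 2 SD drop in the mean would need a drop of 4 SD or more on the remaining days. It is an extreme case.
- **The planning rate is a separate error.** Starting at day 7 leaves out early events, so for the endpoint as written it can only understate events, by about 1.3 at a constant hazard. It is conservative.
- **The 12-month horizon is wrong.** Twelve months from PCI is coherent. The fault lies in where counting starts.
- **Events before discharge certainly count.** The SAP does not list the components of MACE and takes them from CARDIOBASE, so this stays conditional.

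Keeping the endpoint and adding a landmark sensitivity analysis would also expose the bias. But the primary result would still not answer the stated question.

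**Conclusion.** The point holds as a gap in the rules. The endpoint clock starts at PCI, the predictor is complete only 14 days after discharge, and no rule sets the start of event counting. Early events therefore enter or leave the primary analysis according to wear time.

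The expected bias is small: about 2.6 of 66 events in the window, type I error about 5-6% with one or two retained events shifted by up to 1 SD, and almost no change in AUC increase or NRI. These sizes rest on a constant hazard, a base AUC of 0.70 and the assumed shifts in steps. The simulation covers retained events only; the effect of outcome-dependent exclusion is bounded only by the roughly 1.3 events on days 1-7. Strong front-loading of events would enlarge both, but nothing in the SAP shows it. The sample-size arithmetic is sound. The correction should be made because it is nearly free and makes the primary analysis match the stated question.

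**What to change.** Change sections 3.2, 5.1 and 5.2 as follows, before the step data are merged with the registry outcomes at study end.

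1. In the primary analysis include patients who are MACE-free at the end of the 14-day wear window and have valid steps. Count MACE from that landmark to 12 months after PCI.
2. Report MACE before the landmark separately, with the number of patients whose wear was invalid because of an event.
3. Keep the analysis of all events from PCI as a sensitivity analysis.
4. Recount the CARDIOBASE rate over the same interval, and restate expected events and power. At a constant hazard this gives about 63-65 events and power of about 78-80%. The loss does not call for a larger study.

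The cost is SAP wording and one registry recount; the existing day 7-365 count implies that event timing is held. The downside is that a few events leave the primary analysis, and more if events are front-loaded. No extra patients or visits are needed.
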